### **2.3 Data Analysis**

Data were double entered into an Access database and cross checked for discrepancies prior to analysis. Discrepancies were resolved by returning to primary sources. Descriptive

statistics were reported for the demographic and clinical characteristics of the obtained sample, including age, sex, education, employment, baseline function (IPF), baseline severity of PTSD (CAPS and PCL-5), baseline depression (QIDS-SR, MADRS), baseline pain (Pain Score), and baseline post concussive symptoms (NSI). Categorical variables were expressed as frequencies with percentages, and continuous variables as means with standard deviations. To assess how well the samples were randomized, the two active treatment groups were compared on baseline variables including demographics and the outcomes. No missing data imputation was performed. Chi-square tests and Fisher's Exact Test (whenever cell count is less than 5) were used to compare categorical variables; *t-tests were* used to compare continuous variables within and between groups.

For the primary hypothesis, a Welch two-sample t-test that assumes unequal variances was used to investigate whether 1 Hz rTMS versus 10 Hz rTMS provides a significantly greater improvement in PTSD symptoms (CAPS score) and/or function (IPF score) by 30th treatment. Improvement in an outcome was primarily defined as change in scores from pre-treatment baseline to post 30 treatments. The presence of a significant improvement from baseline to post 30 within each treatment group was also tested by performing a paired t-test.

Secondarily, improvement was also evaluated as the proportion of responders and remitters by post 30 treatments. Response was defined as score reduction of 50% (QIDS-SR and MADRS) or 30% (PCL-5 and CAPS-5). Remission was defined using the following score thresholds: 5 or less for QIDS-SR; 10 or less for MADRS; 33 or less for PCL-5; and no longer meeting criteria of PTSD on the CAPS-5. Other secondary analyses were similarly performed on QIDS-SR, pain, NSI, MADRS and PCL-5 scores.

Additionally, sustainability of these treatment effects was investigated using loess (local least square regression), a non-parametric approach suitable for smoothing our numerical vector, of repeated observations. Loess fits least squares regressions to localized subsets of outcome data to produce graphical description of nonlinear empirical relationships (Jacoby, 2000). The graphical displays included smooth curves plus 95% confidence bounds which allowed us to evaluate a statistically significant difference between the mean trajectory over time versus its starting baseline score. We preferred the loess method to the simple pointwise plot of estimates of the mean for two reasons: addition of pointwise 95% confidence intervals will result in less efficient use of data compared to the loess estimates that are based on regressions in local neighborhood of each time point; and an alternative use of standard error of the mean around each estimate is not appropriate for inference as it underestimates the variability between individuals within the study sample (Diong et al., 2018; Nagele, 2003).

The proportions of side effects and dropouts per group were captured. Given the low proportions, a nonparametric binomial test was used to test for significant group difference in their proportions. Two-sided p-values were calculated and used to assess statistical significance defined as  $p < 0.05$ . All statistical analysis was carried out using the R statistical application.

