### **3. RESULTS**

#### **3.1 Patient population**

Participant recruitment, enrollment, assignment to study conditions, and study retention are presented as a Consort diagram in Figure 1. Forty-four participants were enrolled with data

being acquired from September 2014 until February 2018. Nine veterans were not randomized with six failing to meet diagnostic criteria by CAPS-5, one was determined to have a history of seizures, one was unable to get off work, and one was unable to have motor threshold determined. Of the 35 randomized, 17 were allocated to the 1 Hz group and 18 to the 10 Hz group. Of the 17 veterans in the 1 Hz group, 14 completed the primary endpoint and all subsequent visits. The three participants who did not reach the primary endpoint included two that stopped due to work concerns and one who was lost to follow-up. Of the 18 veterans in the 10 Hz group, 13 completed the primary endpoints with one of those not completing the taper or follow-up visits. The five who did not reach the primary endpoint included two that could not tolerate the first treatment, one stopped due to headaches from another medical condition, one was too frustrated by parking, and one was lost to follow-up. A total of 27 who completed the primary end points constituted the final sample for testing the primary hypothesis, and they had no missing data on the tested outcomes.

- Figure 1 about here –

There were no significant differences between treatment groups on their baseline assessment scores, including demographic and baseline rating scales. (Table 1)

- Table 1 about here –

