### **3.4 Tolerability of treatment**

With respect to patient safety, there were no significant events related to the treatment in this trial. There were two Serious Adverse Events (SAE) that were unrelated to the study interventions. There were no seizures and no continuing complications. The 10 Hz group had two participants (2/18 or 11%) that could not tolerate the treatment at the first visit but no such report from the 1 Hz participants (see Figure 1). Exact binomial tests (2-sided) failed to show significant differences between the two randomized groups on the proportions of Veterans who reported headache, site pain during treatment, or stopped treatment due to side effects (Table 4).

- Table 4 about here –

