### **3.5 Post-hoc power calculations**

Given that the final group sample sizes of 14 and 13 (see Figure 1) used to test our primary hypothesis fell short of our anticipated evaluable sample of 40, inadequate statistical power was suspected. Therefore, post-hoc power calculations were performed based on the statistics obtained from the results of t-tests for CAPS-5 (Table 2). Using a paired samples t-test with alpha of 0.05, there were 98% and 76% power (for 10 Hz and 1 Hz groups respectively) to reject the null hypothesis of no difference between the baseline and post-30 scores (that the mean of the paired differences is zero); which support the conclusions reached from our significant results. For the nonsignificant results of 1 Hz versus 10 Hz, however, there was low power to

reject the null hypothesis of no difference in group means using a two-sided two-sample unequal-variance t-test with alpha of 0.05. Therefore, no definitive conclusion can be derived from any failure to reject the null (i.e. non-significant findings) in this study. Although we did not find a definitive conclusion with our study, the preliminary results are that if a difference exists at the group level, it is not likely a large clinical difference.

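### The primary 1 Hz versus 10 Hz comparison rests on 27 completers of 35 randomised, with no missing-data sensitivity analysis described, and section 3.5 qualifies it for low power only

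*Combined protocol and SAP*

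**What the plan says.** Section 2.3 defines improvement as change from baseline to after the 30th treatment. It tests 1 Hz against 10 Hz on CAPS and IPF with a Welch t-test and tests change within each arm with a paired t-test. On missing data its only statement is "No missing data imputation was performed".

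Section 3.1 reports 17 randomised to 1 Hz and 18 to 10 Hz, and then: "A total of 27 who completed the primary end points constituted the final sample for testing the primary hypothesis". It lists each loss by arm and reason. At 1 Hz, two stopped over work and one was lost to follow-up. At 10 Hz, "The five who did not reach the primary endpoint included two that could not tolerate the first treatment"; the other three were one with headaches from another condition, one frustrated by parking and one lost to follow-up.

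Tolerability is handled separately. Section 2.3 says "The proportions of side effects and dropouts per group were captured", and section 3.4 reports "Exact binomial tests (2-sided) failed to show significant differences between the two randomized groups on the proportions of Veterans" with headache, site pain or stopping for side effects.

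Section 3.5 notes that group sizes of 14 and 13 "fell short of our anticipated evaluable sample of 40, inadequate statistical power was suspected". It says that "there were 98% and 76% power (for 10 Hz and 1 Hz groups respectively") for the paired tests, "which support the conclusions reached from our significant results". It draws nothing definitive from the non-significant comparison because of low power, but adds as a preliminary reading that any group difference is probably not clinically large.

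**The concern.** Low power and attrition are different problems. Low power widens the interval around the estimate. Selective loss can move the estimate itself, and a larger completer sample would not correct that. Section 3.5 addresses only the first.

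At least two of the eight losses are tied to the assigned treatment, both at 10 Hz, so the remaining groups may no longer be comparable in the way that randomisation made them. Comparing dropout or side-effect proportions between arms does not show whether the CAPS and IPF results depend on who was lost. The remark in section 3.1 that the 27 had no missing outcome data follows from selecting completers and says nothing about the other eight.

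What is at stake is how far two statements in section 3.5 can be carried: that a large difference is unlikely, and that the power figures back the within-group improvements.

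**Working it through.** **1. Participant flow (section 3.1).** 17 − 3 = 14 and 18 − 5 = 13; 14 + 13 = 27, as reported. Outside the primary test: 8/35 = 22.9%, made up of 3/17 = 17.6% at 1 Hz and 5/18 = 27.8% at 10 Hz (Fisher p = 0.69). Intolerance of the first treatment: 0/17 against 2/18 (Fisher p = 0.49). At these sizes neither p-value is reassuring.

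**2. Completer confidence interval.** Table 2 is not supplied, so the standardised difference d is rebuilt from the p-values in section 3.2, using a pooled t with 25 df as an approximation to Welch. The scale factor is √(1/14 + 1/13) = 0.385.
- CAPS, p = 0.77: |t| = 0.296, so |d| = 0.296 × 0.385 = 0.11. Half-width 2.060 × 0.385 = 0.79. The 95% CI is about −0.68 to 0.91 SD, or its mirror image, because the sign is not visible.
- IPF, p = 0.69: |t| = 0.404, |d| = 0.16, 95% CI about −0.64 to 0.95 SD.

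Before attrition is considered, the data are compatible with a difference of about 0.9 SD in one direction.

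**3. Within-arm effects, in own-arm SDs of CAPS change.**
- 1 Hz, paired p = .03, n = 14: t = 2.436, mean = 2.436/√14 = 0.651.
- 10 Hz, 98% paired power, n = 13: mean = 1.22 if the power was two-sided, 1.09 if one-sided.

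The 76% power figure is not used for 1 Hz. Two-sided, it implies paired p = .013, which conflicts with the reported .03; p = .03 gives about 62% power two-sided and 75% one-sided.

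**4. No change for all eight.** With n completers of mean m and SD s, and k non-completers set to c, let N = n + k. Then M = (nm + kc)/N and S² = [(n−1)s² + n(m−M)² + k(c−M)²]/(N−1).
- 1 Hz, c = 0: M = 14 × 0.651/17 = 0.536, S = 0.937, t = 0.536 × √17/0.937 = 2.36, p = .031.
- 10 Hz, c = 0: M = 13 × 1.216/18 = 0.878, S = 1.010, t = 0.878 × √18/1.010 = 3.69, p = .002 (.003 from the one-sided reading).
- Between groups: solving Welch p = 0.77 gives a 10 Hz/1 Hz SD ratio of 0.61 (10 Hz ahead) or 0.46 (10 Hz behind). After adding the zeros, the difference (10 Hz minus 1 Hz) is +0.002 or −0.164 pooled SD, with p = 0.995 or 0.61. The one-sided reading of the 98% gives 0.60 to 0.99. Even the larger 1 Hz effect implied by 76% takes p no lower than 0.59.
- IPF, assuming SD ratios of 0.5 to 1.1: p about 0.58 to 0.89.

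Mean improvement shrinks to 14/17 = 0.82 and 13/18 = 0.72 of the completer values.

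**5. Worse than no change.** If all eight worsen by 0.25, 0.5 or 1 SD, between-group CAPS p stays at 0.50 or above. With opposite extremes (one arm's non-completers worsen by 1 SD, the other's change like completers), p is 0.09 or above.

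**6. Tipping point for the 1 Hz paired result.** Set t to its critical value, 2.120 on 16 df, and solve for c. At c = −0.226: M = (14 × 0.651 − 3 × 0.226)/17 = 0.496, S = 0.965, t = 0.496 × √17/0.965 = 2.12. Allowing p = .03 to be anything from .025 to .035, the tipping point is a worsening of 0.16 to 0.30 SD.

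Steps 4 to 6 fill in a constant, which understates variance. They show orders of magnitude and do not replace the re-analysis.

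**The case against.** The case against has real force. Nothing is concealed: every loss is listed by arm and reason, and section 3.5 names the 14 and 13 as its basis, so a careful reader knows that these are completer results. Its heading is post-hoc power, so a discussion of power belongs there, and the supplied text ends with that section. An attrition caveat may appear in a later discussion. CAPS was scheduled only at baseline and after the 30th treatment (section 2.2.3), so no method can recover much for CAPS. The one result that moves easily is a secondary within-group test. All of this stands, and it is why the point is minor.

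What remains is that an efficacy inference is drawn in section 3.5 itself, with only one of its two limits stated.

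A reader might go further and infer that leaving out the eight hides a true difference between frequencies, that the bias favours 10 Hz, or that the 1 Hz improvement is spurious. The documents support none of these. The comparison stays non-significant in every scenario tried, the direction of bias is unknown, and the stated 1 Hz reasons (work, loss to follow-up) do not indicate worsening.

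**Conclusion.** The point holds and is minor. The primary comparison is a completer analysis of 27 of 35, no sensitivity analysis for the other eight is described in the supplied text, and section 3.5 qualifies its reading for power alone. The suggestion that a large difference is unlikely is poorly supported, first by precision (the CAPS interval reaches about 0.9 SD) and then by attrition of unknown effect. The between-group null is not overturned. The 1 Hz within-group result has a thin margin, which would matter only if its three non-completers had in fact worsened.

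The sizes rest on values rebuilt from rounded p-values and one post-hoc power figure, on the pooled-t approximation for the interval, and on constant imputation. Table 2 would allow the interval and the filled-in figures to be computed directly.

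**What to change.** 1. Keep the Welch test and label it a completer analysis. Add one sensitivity analysis of CAPS and IPF change in all 35 by allocated arm. Use multiple imputation from baseline and any available PCL-5 or IPF scores, with delta shifts centred on no change and on 0.25 to 1 SD worsening, so that imputation variance is carried. For the two who did not tolerate the first treatment, this will rest essentially on baseline data and the chosen shift.
2. In section 3.5, give the 95% CI of the between-group difference and withdraw or qualify the statement about a large difference in its light. State that this and the within-group results apply to completers and are limited by attrition as well as by low precision. If a later discussion already says so, a cross-reference is enough.

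The cost is a short re-analysis of existing data and a few sentences, with no new data collection. The drawbacks are that the missing-data assumptions cannot be tested and that the mean improvements will look smaller (by factors of about 0.82 at 1 Hz and 0.72 at 10 Hz under no change).

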## **2.2 Procedures**

2.2.1 Overview: The screening/baseline visit began by acquiring written informed consent.

Subsequently, evaluations to determine safety and appropriateness, as well as clinical ratings and laboratory testing (Urine Drug Screen (UDS) and urine pregnancy testing) were performed.

Those meeting eligibility criteria, including ability to obtain motor threshold, were randomized to 1 Hz versus 10 Hz stratified by significant depression (Montgomery-Asberg Depression Rating Scale (MADRS) (Montgomery and Asberg, 1979) > 19). Participants were treated for 5

days a week for 6 weeks with a 3 week taper (3 treatments per week for 1 week, 2 treatments per week for 1 week, then 1 treatment per week for 1 week). Participants underwent clinical evaluation weekly for clinical effect during the treatment, at the end of the taper and at 1 and 3 months post treatment. In addition, safety was assessed prior to each treatment and/or evaluation.

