2.2.4 Repetitive Transcranial Magnetic Stimulation: The veterans were placed in the NeuroStar chair (Neuronetics, Malvern, PA) with hearing protection in place, and the motor threshold (MT) was determined. The MT was defined as the stimulus intensity of stimulation that induces visually perceptible movement of the contralateral (in this case, the left) abductor pollicis brevis (APB) 50% of the time. (Pridmore et al., 1998). Once the spot of maximal contraction was determined, a PEST algorithm (Mishoury et al., 2004) was used to determine the MT four times. The mean of these four MT served as the MT used in the study. After motor threshold determination, a stratified randomization was performed based on significant depressive symptoms, which were defined as a MADRS score > 19. Using a computer randomization schedule, an investigator who was independent of any treatments generated two random lists of active and sham index cards (i.e., with and without significant depression) that were placed in envelopes prior to the trial beginning. When the participant was ready to begin the first treatment, the treater opened the next envelope in line for the appropriate group to determine the randomization assignment. The participant knew the assignment as well as the treater but the investigators assessing all the clinician rating scales were masked to assignment.

After the randomization, the stimulator coil was positioned over the dorsolateral prefrontal cortex - DLPFC (Brodmann Area 9/46). The right dorsolateral prefrontal cortex was targeted using head measurements and a computerized program that provides coordinates for the approximate F4 electrode site under the 10/20 electrode convention (Beam et al., 2009). The dose of rTMS over the DLPFC was 110% of MT. The intensity of 110% MT was chosen as our sample was limited to 18-50 years of age. The 110% MT was thought to be a reasonable option

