### **3.2 Effects at the end of 30 treatments**

The results of the two-sample t-tests failed to reject the null hypothesis of no significant difference between the two treatment groups (Table 2) in improvement on the CAPS ( $p = 0.77$ ) and IPF ( $p = 0.69$ ) scores from baseline to post-30.

- Table 2 about here –

The secondary analyses, however, yielded some significant findings with respect to the primary outcomes (Table 2). For the 1 Hz group, a paired t-test indicated that PTSD symptoms as measured by CAPS scores were significantly lower by the 30th treatment (improved,  $p = .03$ ). The scores on MADRS, PCL-5, and QIDS-SR also significantly improved. The change in function as measured by the IPF, however, did not quite reach significance ( $p=0.075$ ) in the 1 Hz group. In contrast, the 10 Hz group demonstrated significant improvement from baseline to the 30th treatment on all outcomes listed except pain score. (Table 2) Similarly, there was failure to reject the null hypothesis of no relationship between the groups on either response or remission rate by 30th treatment (Table 3).

- Table 3 about here –

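### The primary Welch test on change scores leaves out the MADRS stratum used to randomise and fixes the baseline slope at 1; no adjusted estimate is planned, at a likely but assumption-dependent cost in precision

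*Combined protocol and SAP*

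**What the plan says.** All references are to the combined protocol and SAP.

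- **Randomisation.** In Section 2.2.1 participants are "randomized to 1 Hz versus 10 Hz stratified by significant depression". Section 2.2.4 repeats that "a stratified randomization was performed based on significant depressive symptoms, which were defined as a MADRS score > 19", with a separate list for each stratum. No blocking is described.
- **Primary analysis (Section 2.3).** "a Welch two-sample t-test that assumes unequal variances was used to investigate whether 1 Hz rTMS versus 10 Hz rTMS provides" greater improvement in CAPS and/or IPF by the 30th treatment. "Improvement in an outcome was primarily defined as change in scores from pre-treatment baseline to post 30 treatments".
- **Use of baseline data (Section 2.3).** Apart from the subtraction, baseline values are described and tested between groups: "To assess how well the samples were randomized, the two active treatment groups were compared on baseline variables".
- **Other analyses (Section 2.3).** These are paired t-tests, responder and remitter proportions, the same tests on secondary scales, loess curves and binomial tests. None contains the stratum or a baseline covariate.
- **Results.** "A total of 27 who completed the primary end points constituted the final sample for testing the primary hypothesis" (Section 3.1), split 14 and 13. The primary tests "failed to reject the null hypothesis of no significant difference between the two treatment groups" (Section 3.2), with p = 0.77 for CAPS and 0.69 for IPF. Section 3.5 concedes low power for this comparison, but adds as a preliminary reading that "if a difference exists at the group level, it is not likely a large clinical difference".

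**The concern.** A factor judged important enough to stratify on is normally carried into the estimate. Here it is not. Subtraction does deal with chance imbalance in the baseline value of the outcome, but only correctly if the true slope of post on baseline is 1. Imbalance in the stratum is not dealt with at all, and a between-group significance test at baseline adjusts nothing.

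Stratified lists do not guarantee balance in the analysed set. Blocking is not stated, and 8 of the 35 randomised patients (23%) are not analysed.

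This is about precision and about imbalance in the realised sample. It is not a bias over repeated randomisation. It matters because the remark in Section 3.5 that a large difference is unlikely depends on how wide the interval for the group difference is, and the sample is small.

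**Working it through.** **Inputs from the documents.** Analysed groups of 14 and 13; two-sided alpha 0.05; CAPS p = 0.77 and IPF p = 0.69; anticipated evaluable sample 40. That 40 cannot be reproduced, because no effect size, SD or target power is given with it.

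**Inputs assumed.** The baseline-to-post correlation rho; k = baseline SD / post SD; the stratum's effect and its split (about half and half). Tables 1 and 2 are not in the text available.

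**1. The reported comparison.** On 25 df, p = 0.77 gives |t| = 0.296. The standard error in change-score SD units is sqrt(1/14 + 1/13) = 0.385.

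- Difference: 0.296 × 0.385 = 0.114 SD (sign arbitrary).
- 95% half-width: 2.06 × 0.385 = 0.793, so the interval is about −0.68 to 0.91 SD.
- Power at the observed differences is about 6% (CAPS) and 7% (IPF), which agrees with the low power conceded in Section 3.5.

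**2. Variance of the adjusted estimate relative to the change-score estimate, stratum not prognostic.**

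Ratio = (1 − rho²) / (1 + k² − 2·rho·k), multiplied by (N − 3)/(N − 5) = 24/22 = 1.091 for two covariates at N = 27.

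Example, k = 1 and rho = 0.5: 0.75/1.00 × 1.091 = 0.818, with square root 0.905.

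Break-even at k = 1: (1 + rho)/2 × 1.091 = 1, so rho = 0.83.

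**3. Simulation at 14 v 13.** The true difference is 0.909 change-score SD, which is what 20 per group (an assumed even split of the 40) would detect with 80% power. Welch power is about 62% throughout. The adjusted model uses ordinary model-based standard errors.

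| k | rho | Variance ratio | CI width v Welch | Adjusted power |
|---|---|---|---|---|
| 1 | 0.3 | 0.709 | 0.84 | 77% |
| 1 | 0.5 | 0.818 | 0.90 | 71% |
| 1 | 0.7 | 0.927 | 0.96 | 65% |
| 0.85 | 0.3 | 0.819 | 0.90 | 71% |
| 0.85 | 0.5 | 0.938 | 0.97 | 65% |
| 0.85 | 0.7 | 1.045 | 1.02 | 60% |
| 0.7 | 0.3 | 0.928 | 0.96 | 65% |
| 0.7 | 0.5 | 1.036 | 1.02 | 61% |
| 0.7 | 0.7 | 1.091 | 1.04 | 58% |

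The width ratios are against Welch's own, data-dependent degrees of freedom. Against a fixed 25 df (23 for the model) they run from 0.85 to 1.05.

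**4. If the stratum predicts outcome.** With the stratum explaining 15% of the remaining variance, the adjusted interval is narrower in all nine cells (ratio 0.77 to 0.96), with power from about 65% to 83%.

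A separate run used a larger stratum effect, a shift of one baseline SD in the post score, and a difference of 1.1 SD (in units of the change-score SD without the stratum shift):

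- Lists balanced by blocking: Welch's type I error falls to 1.8–2.8%, and its power is 63–70% against 76–88% adjusted.
- Unblocked lists: Welch's type I error stays near 5%, and its power is 60–65% against 73–84% adjusted.

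**5. Effect on the CAPS interval.** If the point estimate stays at 0.114 and k = 1, the half-width of 0.793 becomes 0.671, 0.721 or 0.767 at rho 0.3, 0.5 or 0.7. In the best of these the upper limit moves from 0.91 to about 0.78 SD.

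**The case against.** The strongest reply is that nothing here is invalid. Welch on change is a legitimate test under randomisation, and the gain depends on quantities the documents do not give. In three of the nine cells adjustment lowers power. Entry required a PCL-5 of at least 45 and a PTSD diagnosis on the CAPS, which may compress baseline CAPS and push k below 1, where the gain shrinks or reverses. All of this stands as a limit on size. It is inference for CAPS, applies less to IPF, and assumes a stratum that predicts nothing.

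Second, there is reason to keep Welch. The 98% and 76% within-group powers in Section 3.5, combined with p = 0.77, imply that the 1 Hz change SD is roughly 1.4 to 2.0 times the 10 Hz one. Model-based standard errors give up some protection against this: type I error is about 5.4% or 5.8% if residual SDs differ 1.5- or 2-fold. It stays near 5% when the larger arm is the more variable, as these figures suggest. HC3 standard errors restore protection, but in six of the nine cells their power is below Welch's. For example, at k = 1 HC3 power is 71%, 65% and 59% at rho 0.3, 0.5 and 0.7. This is why Welch should stay and HC3 should be a sensitivity analysis.

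Third, Section 3.5 does say that no definitive conclusion can be drawn, and Section 3.1 reports no significant baseline differences. Both are fair to note. But non-significance at this size does not show balance, and the remark about a large difference is still made without an interval.

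**Conclusion.** The concern holds as a suggestion for improvement. The documents stratify on MADRS above 19 and never use the stratum in an estimate, and baseline enters the primary comparison only with a slope fixed at 1.

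With a non-prognostic stratum the change in interval width runs from 16% narrower to 4% wider over the grid examined. The gain is largest at low correlation with equal SDs and vanishes as the true slope approaches 1. A prognostic stratum shifts the balance further towards adjustment. The correlation, SD ratio, stratum effect and 0.909 SD difference are all assumptions.

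The reported conclusion of no demonstrated difference would probably not change. With the same CAPS point estimate, even a variance ratio of 0.65 raises t only from about 0.30 to 0.37 (p about 0.72). The estimate itself could shift if the analysed groups were imbalanced, which cannot be checked without Tables 1 and 2.

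**What to change.** **For this trial.** Add, for CAPS and for IPF, a linear model of the post-30 score on group, baseline value of the same outcome and MADRS stratum (above 19 or not), with ordinary model-based standard errors. Report the adjusted difference with its 95% interval. Because results are already reported, keep Welch as the reported primary test, label the adjusted model post hoc, and give HC3 standard errors as a further sensitivity analysis. Drop the baseline p-values and let the descriptive table stand.

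**For any follow-on protocol.** Prespecify the adjusted model as primary, with Welch and HC3 as sensitivity analyses.

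**Cost.** One extra model per outcome in R on data already collected, and two degrees of freedom. There is a small loss of power if the true baseline slope is near 1 and the stratum is not prognostic, and some loss of Welch's protection against unequal variances.
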